7.4 PRIMARY ENDPOINT

The primary endpoint of this study is PFS, defined as the time (weeks) from the date of randomisation to the date of disease progression, or date of death whichever is earlier, subjected to the censoring rule (see [Table 7.4: 1](#)). The date of progression for the primary analyses will be determined based on an independent central imaging review incorporating both radiologist and oncologist reviews, blinded to treatment assignments. The primary endpoint analysis will be performed on the randomised set of patients.

A stratified log-rank test will be used to test the effect of afatinib on PFS compared to erlotinib. The test will be stratified by race (Eastern Asian and Non-Eastern Asian). An interim analysis is planned using Haybittle-Peto stopping boundary (p-value < 0.0001). The details of the interim analysis are described in the DMC SAP. The final significance level need not be adjusted in the case of one interim look. The final significance level will be adjusted as necessary in case additional interim looks are requested by the DMC.

A Cox proportional hazard model, stratified by race will be used to estimate the hazard ratio and 95% confidence interval (CI) between the two treatment groups. Kaplan-Meier estimates and 95% CIs (using Greenwood's standard error estimate) will be tabulated at time points of

every 12 weeks and will include a comparison of the treatment groups using a z-test (approximation of the normal distribution). Kaplan-Meier curves for the two treatment groups will also be produced.

A descriptive analysis of PFS will be performed at the time of the final analysis.

The rules to determine whether or not patients have had a PFS event (progression or death) along with the date of event or date of censoring (for those with no event) are specified in Table 7.4: 1. These rules will be applied to both the independent central review and investigator assessed data prior to analysis. A summary table of the reasons for censoring will be produced by treatment group.

Table 7.4: 1 Rules to determine events and censoring for PFS

Rule #	Situation	Outcome (event or censored)	Date of PFS event or censoring
1	No baseline tumour assessment (no death before second scheduled assessment)	censored	Date of randomisation
2	Progressed from central imaging (no missed radiologic assessments)	event	Date of PD
3a	Non-PD from central imaging ¹ , death before next scheduled assessment	event	Date of death
3b	Non-PD from central imaging ¹ , one missed assessment, death or progression after date of missed assessment, but before a second scheduled assessment	event	Date of PD or death
3c	Non-PD from central imaging ¹ , more than one consecutive missed assessment, death or progression after date of second missed assessment	censored	Date of last imaging before missed assessment
3d	Non-PD from central imaging ¹ , more than one consecutive missed assessment, non-PD according to imaging after missed assessments	censored	Date of last non-PD imaging
4	New anti-cancer medication before progression or death	censored	Date of last imaging before new anti-cancer medication
5	Death before the scheduled date of first imaging	event	Date of death
6a	No imaging performed post-baseline, patient dies between first and second scheduled assessments	event	Date of death
6b	No imaging performed post-baseline, patient dies after second scheduled assessment	censored	Date of randomisation
6c	No imaging performed post-baseline, vital status is unknown or patient known to be alive	censored	Date of randomisation
7	Alive and not progressed from central imaging (no missed assessments)	censored	Date of last imaging

¹ - From the last assessment at which CR, PR or SD was assessed.

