\*\*\* Randomization into the study via the IXRS is permitted up to 2 days prior to the C1V1 if site procedures require advance randomization to accommodate the logistics of dispensing study medication to patients. Sites that use this option must include a copy of this policy in the ISF and submit a copy to the sponsor.

\*\*\*\* Except as noted for ECHO or MUGA and tumour assessments

ax is the course number in CxV1

by is the visit number in Opy

1. Randomization into study does not need to be delayed for shipment of tumour sample; however, availability of tumour sample for shipment to central laboratory must be confirmed prior to randomization and shipped within 28 days of randomization.
2. Includes height (at screening only) and weight.
3. Limited physical examination to capture clinical assessment of ongoing or new adverse events and monitor for signs and symptoms of clinical response.
4. A 12-lead resting digital electrocardiogram (ECG) will be performed at Screening to establish a baseline assessment, at C1V2 (Day 8 of treatment), at the start of every third course thereafter (C4, C7, etc.) and EOT. After approval of Protocol Version 3.0, ECG will only be performed if clinically indicated.
5. Includes hematology, serum biochemistry, and urinalysis. Refer to the Investigator Site File (ISF).
6. ECHO or MUGA (At German sites, only ECHO is allowed) will be performed during screening, at Course 4 and then at every third course (Course 7, 10, 13 etc.), and at EOT (if not performed in the previous 8 weeks). Requirement for EOT ECHO or MUGA may be waived for patients meeting all of the following criteria: 1) too sick from their disease or disease related symptoms to travel in the opinion of the investigator, 2) have had evidence of stable LVEF on the previous scheduled post treatment assessment and 3) have no evidence of cardiovascular disease. For LVEF evaluations, the assessment can occur  $\pm 7$  days of the scheduled Day 1 of the corresponding course.  
After approval of Protocol Version 3.0, ECHO or MUGA will only be performed if clinically indicated.
8. Blood sample will be collected and plasma will be sent to logistics laboratory at baseline (C1V1), C2, and at EOT or determination of disease progression. After approval of Protocol Version 3.0, the collection of blood sample at EOT will no longer be required.

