### 3.3.2 Inclusion criteria

1. Diagnosis of advanced stage NSCLC considered to be squamous histology, including mixed histology, in the opinion of the investigator.
  2. Completion of at least 4 cycles of platinum-based doublet chemotherapy, with or without additional [non-EGFR] targeted agents, as 1st line treatment of Stage IIIB/IV NSCLC. *Note* the below scenarios are also considered to meet this requirement:
    - a. Patients relapsing within 6 months of completing adjuvant/neo-adjuvant/curative -intent chemotherapy/chemoradiotherapy (*Note:* these patients are still required to have had the equivalent of 4 cycles of platinum-based doublet chemotherapy except in setting noted below).
- OR
- b. Patients intending to receive four cycles of platinum-based doublet chemotherapy but due to toxicity, and not PD, discontinue just the platinum agent after at least two cycles of platinum doublet had been administered.
  3. Eligible to receive 2nd line therapy in the opinion of the investigator. Patients who received non-EGFR based therapy for maintenance are eligible.
  4. Measurable disease according to RECIST 1.1 ([R09-0262](#)). Refer to [Appendix 10.1](#).
  5. Eastern Cooperative Oncology Group (ECOG) score of 0 or 1 ([R01-0787](#)). Refer to [Appendix 10.2](#).
  6. Availability of tumour tissue material for correlative studies (refer to [Section 5.6](#)). Archived tumour tissue is acceptable.
  7. Adequate organ function, defined as all of the following:
    - a. LVEF >50% or within institution normal values.
    - b. Absolute neutrophil count (ANC) > 1500 / mm^3. (ANC >1000/mm^3 may be considered in special circumstances such as benign cyclical neutropenia as judged by the investigator and in discussion with the sponsor).
    - c. Platelet count >75,000 / mm^3.
    - d. Estimated creatinine clearance > 45ml / min. Refer to [Appendix 10.3](#).

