#### 5.2.5.2 Vital Signs

Vital sign measurements- blood pressure [systolic blood pressure, diastolic blood pressure], pulse rate, respiratory rate, temperature, measurement of height (in cm, at screening) and body weight (in kg), and the evaluation of the ECOG performance status will be performed at the times specified in the flow chart.

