### 7.3.1.1 Primary endpoint PFS

The primary analysis of PFS will be conducted after 372 patients have progressed or died.

Disease progression will be evaluated according to the RECIST 1.1 criteria ([R09-0262](#)). The analysis will be based upon the evaluation of tumour imaging as determined by central imaging. Clinical deterioration without image-based progression will be excluded from the primary analysis, but will be examined as part of a sensitivity analysis.

For patients with known date of progression (or death):

- PFS [days] = date of progression or death – date of randomisation + 1.

Patients with unknown disease progression status or date, or who are treated with new anti-cancer therapy will be handled as described in [Section 7.4](#).

A stratified log-rank test will be used to compare afatinib to erlotinib. The test will be stratified by race (Eastern Asian vs. non-Eastern Asian).

A stratified Cox proportional-hazards model will be used to derive the hazard ratio and 95% confidence interval (CI) between the two randomised regimens. Kaplan-Meier estimates and 95% CI will be calculated at landmark time points.

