## 7.6 DETERMINATION OF SAMPLE SIZE

[Table 7.6: 1](#) shows the number of PFS events required for the primary analysis. The Table indicates that 372 PFS events would be expected to provide 90% power for the log-rank test,

Proprietary confidential information.

© 2016 Boehringer Ingelheim International GmbH or one or more of its affiliated companies. All rights reserved.

This document may not - in full or in part - be passed on, reproduced, published or otherwise used without prior written permission.

presuming a hazard ratio of 0.714 for afatinib relative to erlotinib (corresponding to median PFS times of 14 vs. 10 weeks, respectively). Data on file ([R10-6208](#)).

Table 7.6: 1 Number of PFS events required for 80% and 90% power

	80% Power	90% Power
Median PFS for afatinib	14 weeks	14 weeks
Median PFS for erlotinib	10 weeks	10 weeks
Hazard ratio of afatinib vs erlotinib	0.714	0.714
Number of events required for both groups 	278	372
Total Number of randomised patients	350	500

 log-rank test, alpha = 0.05, two-sided

 The number of required events was calculated using EAST-5 software excluding interim analysis, with patients randomised in a 1:1 ratio at a rate of 6 patients per week.

Table 7.6: 2 indicates that 632 deaths would be expected to provide 80% power for the log-rank test, presuming a hazard ratio of 0.800 for afatinib relative to erlotinib (corresponding to median survival times of 8.75 vs. 7.00 months, respectively).

Table 7.6: 2 Number of deaths required for 80% and 90% power

	80% Power	90% Power
Median OS for afatinib	8.75 months	8.75 months
Median OS for erlotinib	7.00 months	7.00 months
Hazard ratio of afatinib vs erlotinib	0.80	0.80
Number of events required for both groups 	632	845
Total Number of randomised patients	800	1040

 log-rank test, alpha = 0.05, two-sided

 The number of required events was calculated using EAST-5 software excluding interim analysis, with patients randomised in a 1:1 ratio at a rate of 36 patients per month.

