6.7 BASELINE, TIME WINDOWS AND CALCULATED VISITS

Baseline values will be the measurements taken most recently prior to first administration of study drug.

Study day will be calculated relative to the date of the first administration of study drug. The day prior to first administration of study drug will be ‘Day -1’ and the day of first administration of study drug will be ‘Day 1’; therefore ‘Day 0’ will not exist.

For the presentation of tumour response data which will follow a calculated visit approach based on the protocol specified tumour imaging schedule. Imaging will be performed at week 8, 12 and 16, and in 8-weekly intervals thereafter from the date of randomisation; images will be slotted to Week 8, 12, 16, 24, ... XX based on their relative day and using a $\pm 2, \pm 4$ week window as appropriate (images taken in the first 4 weeks from randomisation will be slotted to Week 8). If two or more images for a patient are assigned to one interval then the last assessment will be used to ensure progressive disease is not missed. Note German sites only will have an X-ray completed instead of a CT or MRI for the week 12 assessment. If disease progression is suspected, a follow-up CT or MRI will then be completed. In the case where a CT or MRI is not completed for the week 12 assessment, it will be handled as missing assessment.

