7.5 SECONDARY ENDPOINTS

7.5.1 Key secondary endpoint

Overall survival, defined as the time from randomization to death, is the key secondary endpoint.

A Cox proportional hazard model, stratified by race, will be used to estimate the hazard ratio and the corresponding 95% confidence interval. Additionally, a stratified log-rank test will be performed. Kaplan-Meier estimates of OS and 95% CIs (using Greenwood's standard error estimate) will be tabulated at 12-week interval and compared at each time point with z-test. Kaplan-Meier curves will be presented graphically.

OS will be analysed twice. The first analysis will be performed at the time of the primary PFS analysis using a Haybittle-Peto stopping boundary (p-value <0.0001). The primary analysis of survival is planned at 632 deaths. However, if the futility analysis of PFS curtails accrual at 500 patients, the primary analysis of OS will be performed after 80% of the randomized patients have died.

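### PFS and OS are tested with race as the only stratum; adding screening ECOG (0 vs 1), already collected, would gain about 1 to 5 points of power if ECOG is clearly prognostic

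*SAP*

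**What the plan says.** For PFS, protocol 7.3.1.1 ("The test will be stratified by race (Eastern Asian vs. non-Eastern Asian")) and SAP 7.4 ("The test will be stratified by race (Eastern Asian and Non-Eastern Asian")) name race as the only stratum. The PFS Cox model is stratified likewise. For OS, SAP 7.5.1 reads: "A Cox proportional hazard model, stratified by race, will be used to estimate the hazard ratio". It adds a stratified log-rank test without naming strata, and race is the only one defined. Protocol 4.1.2 and 7.5 stratify the randomisation by race alone.

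ECOG is available before treatment. Protocol 3.3.2 requires an "Eastern Cooperative Oncology Group (ECOG) score of 0 or 1", and protocol 5.2.5.2 says "the evaluation of the ECOG performance status will be performed at the times specified in the flow chart". The flow chart marks performance status at screening and at C1V1. The only use of ECOG in the SAP text available is a descriptive by-visit summary (SAP 7.8.5).

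Protocol 7.6 sizes PFS at 372 events for 90% power, "presuming a hazard ratio of 0.714 for afatinib relative to erlotinib", and OS at 632 deaths for 80% power at a hazard ratio of 0.80. Both use two-sided 5% tests.

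**The concern.** If a baseline factor is prognostic and is left out of a log-rank test, patients with different underlying hazards share the same risk sets. The estimated effect is then pulled towards 1 and power is lost. Stratifying by the factor compares like with like and recovers much of that loss.

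OS is planned at 80% power, with no margin. It is tested only if PFS is significant (protocol 7.1 and 7.3.2), so PFS power carries through to OS. If accrual is curtailed at 500 patients, OS is analysed after 80% have died, which is 0.8 × 500 = 400 deaths. Power there, by the same formula as for the full trial, is only 60.7% at a hazard ratio of 0.80. A stratum built from a value already on file could give some of the benefit of extra events without enrolling anyone.

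**Working it through.** **1. The plan's own figures.** With 1:1 allocation and two-sided α = 0.05, power = Φ(½·√D·|ln HR| − 1.960).

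- PFS: D = 372, HR = 10/14, |ln HR| = 0.3365. ½ × 19.29 × 0.3365 = 3.245; 3.245 − 1.960 = 1.285; power 90.1%.
- OS: D = 632, HR = 0.80, |ln HR| = 0.2231. ½ × 25.14 × 0.2231 = 2.805; 2.805 − 1.960 = 0.845; power 80.1%.

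The stated figures reproduce without ECOG.

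**2. Comparing the two tests.** The statistic is Z = Σ(O − E)/√ΣV, summed over strata: two strata (race) against four (race × ECOG), on the same simulated data.

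- From protocol 7.6: control medians 10 weeks and 7.0 months; 372 events of 500 patients at 6 per week; 632 deaths of 800 patients at 36 per month.
- Assumed, because the documents do not say: 50%, 67% or 80% ECOG 1; 20% Eastern Asian; blocks of 4; exponential times; a constant treatment effect.
- Protocol 7.6 states whole-population effects. When ECOG is prognostic, the within-ECOG treatment hazard ratio was therefore lowered (PFS 0.694–0.711, OS 0.785–0.798) to hold race-only power near plan. Achieved race-only power was 89.3–90.0% for PFS and 79.9–80.9% for OS.
- 24,000 trials per setting; Monte Carlo standard error of each power 0.2–0.3 points.

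Change in power (percentage points) from adding ECOG, over the three ECOG splits:

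| ECOG 1 vs 0 HR | PFS | OS |
|---|---|---|
| 1.0 | −0.6 to −0.5 | −0.3 to −0.2 |
| 1.2 | −0.3 to 0.0 | −0.1 to 0.0 |
| 1.5 | +0.7 to +1.2 | +1.2 to +1.6 |
| 2.0 | +2.6 to +3.3 | +3.3 to +5.2 |

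At 67% ECOG 1, PFS power goes from 89.8% to 90.9% (HR 1.5) and from 89.9% to 93.1% (HR 2.0). OS goes from 80.5% to 81.9% and from 80.6% to 85.0%.

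**3. In terms of events.** The equivalent ratio of events is [(1.960 + z₂)/(1.960 + z₁)]², where z is the normal quantile of each power. For OS at HR 2.0 and 67% ECOG 1: [(1.960 + 1.036)/(1.960 + 0.863)]² = 1.13, or about 13% more events. Over all splits the gain equals about 3–5% more events at HR 1.5 and 9–16% at HR 2.0.

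**4. Type I error.** In null runs at 67% ECOG 1 and ECOG HR 1.5 or 2.0, rejection was 5.0–5.3% (race) and 5.0–5.2% (race × ECOG).

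**5. Second simulation.** This used 22% Eastern Asian and 6,000–8,000 trials per setting.

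- Race-only power held near plan, 60% ECOG 1: +1.2 (PFS) and +2.1 (OS) at HR 1.5; +3.2 and +5.0 at HR 2.0.
- 0.714 and 0.80 read instead as within-ECOG effects, 50–80% ECOG 1: PFS +0.1 to +1.1 and OS +1.4 to +1.9 at HR 1.5; PFS +3.0 to +4.9 and OS +3.3 to +6.0 at HR 2.0; between −0.4 and +0.4 at HR 1.2–1.3. On this reading race-only OS power at HR 2.0 and 60% ECOG 1 is 74.1%, and ECOG strata bring it to 79.7%.
- Curtailed trial (400 deaths), same reading, 60% ECOG 1: OS 58.0% to 60.1% at HR 1.5 and 54.6% to 60.7% at HR 2.0.

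**6. Interim (130 events in the first 176 patients).** 12,000 trials per setting, 67% ECOG 1. Mean Z, race vs race × ECOG: −1.91 vs −1.88 at ECOG HR 1.0, −1.94 vs −1.95 at 1.5, −1.95 vs −2.04 at 2.0.

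**The case against.** The plan analyses by exactly the factor used to randomise, its power figures reproduce, its type I error is sound and no sections conflict. That stands: the race-only analysis is valid, and this is an efficiency choice.

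The documents do not say that ECOG 0 vs 1 is prognostic here, and they give no split. This also stands. At an ECOG hazard ratio near 1.3 the gain is nil or close to it: further PFS runs at 1.3 gave −0.2 to +0.3 points, and another set at 67% ECOG 1 gave +0.2 for PFS and +0.6 for OS. At 1.5 the PFS gain is about one point at best. The 5-point end of the range applies to OS at a hazard ratio of 2.0, not to PFS as planned.

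The OS gains are idealised. Protocol 7.3.2 expects post-progression treatment to mask the effect on OS, whereas the simulation holds it constant. Imposing the actual scan schedule and dropout on PFS did not materially change the result.

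The tumour shrinkage ANCOVA in SAP 7.5.2.2 adjusts for a baseline value that is not a randomisation stratum. It is only a weak precedent, because that value is the baseline of the same measurement.

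SAP 6.4, SAP 7.6 and protocol 7.3.2.1.1 are not visible, so supportive or subgroup use of ECOG cannot be excluded; the main tests are race-only either way. Protocol section 11 (global amendment 2) says PFS has been reported, so in this trial an ECOG-stratified test could now only be supportive. That limits what can still be done; it does not bear on whether the plan would have been better with ECOG.

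**Conclusion.** The point holds as a low-cost improvement, not as an error. The gain is about 1 to 5 points of power if the ECOG 1 vs 0 hazard ratio is between about 1.5 and 2.0: roughly 1 to 3 points for PFS and 1 to 5 for OS. It is essentially nil at 1.3 or below, with a loss of about 0.2 to 0.6 points if ECOG has no prognostic effect. These figures rest on the assumed ECOG split and prognostic effect and on constant hazard ratios. The possible loss is small compared with the possible gain. With two ECOG levels there are only four strata, so sparse strata are not a practical worry at 372 or 632 events.

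**What to change.** In SAP 7.4 and 7.5.1, and protocol 7.3.1.1 and 7.3.2, specify before unblinding that the log-rank tests and Cox models for PFS and OS are stratified by race and ECOG (0 vs 1).

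- **Which value.** Use the screening ECOG recorded before randomisation, not the SAP 6.7 baseline ("Baseline values will be the measurements taken most recently prior to first administration of study drug"). The trial is open-label and "Randomization into the study via the IXRS is permitted up to 2 days prior to the C1V1", so a C1V1 score could be recorded with the allocation known. The SAP 6.7 baseline is also undefined for randomised patients who are never dosed, and they belong to the Randomised Set.
- **Other values.** State a rule, for example that a missing screening ECOG or one above 1 is counted in the ECOG 1 stratum.
- **Sensitivity.** Report the race-only analysis alongside.
- **Interim.** State in the DMC SAP whether the interim test stays race-only. It can, since the choice hardly changes the statistic.

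The cost is SAP and protocol wording and one variable already collected. The hazard ratio becomes conditional on ECOG as well as race, and the small power loss given above applies if ECOG is not prognostic.

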7.5 SECONDARY ENDPOINTS

7.5.1 Key secondary endpoint

Overall survival, defined as the time from randomization to death, is the key secondary endpoint.

A Cox proportional hazard model, stratified by race, will be used to estimate the hazard ratio and the corresponding 95% confidence interval. Additionally, a stratified log-rank test will be performed. Kaplan-Meier estimates of OS and 95% CIs (using Greenwood's standard error estimate) will be tabulated at 12-week interval and compared at each time point with z-test. Kaplan-Meier curves will be presented graphically.

OS will be analysed twice. The first analysis will be performed at the time of the primary PFS analysis using a Haybittle-Peto stopping boundary (p-value <0.0001). The primary analysis of survival is planned at 632 deaths. However, if the futility analysis of PFS curtails accrual at 500 patients, the primary analysis of OS will be performed after 80% of the randomized patients have died.

7.5.2 Other Secondary endpoints

7.5.2.1 Best RECIST assessment

Each patient will be assigned to one of the following RECIST categories, CR, PR, SD, Non-CR/Non-PD (NN), PD or Not Evaluable (NE), irrespective of protocol violations or missing data.

Objective response is defined as CR or PR. Time to objective response is the time from randomization to the date of first documented CR or PR. The duration of objective response is the time from first documented CR or PR to the time of progression or death. Disease control is defined as CR, PR, SD or NN. The duration of disease control is the time from randomization to progression or death defined only for those patients with disease control.

Logistic regression, stratified by the same stratification factors used for the analysis of PFS, will be used to test for a difference between regimens for objective response and for disease control based on central imaging assessment. Nominal significance levels will be reported.

Time to response will be summarised by the planned imaging time points. Descriptive statistics will be calculated for the duration of objective response and duration of disease control, where applicable patients will be censored as for the PFS primary analysis.

A summary of objective response rate and disease control rate using the investigator assessment of best overall response will also be produced, along with a table comparing the investigator best overall RECIST assessment with the corresponding central imaging assessment.

The impact on objective response for each of the subgroups defined in [Section 6.4](#) will be explored. The logistic model detailed above but without the stratification factors will be used. A ‘forest plot’ will be provided presenting the odds ratio (Afatinib vs. Erlotinib) and corresponding 95% CI for each subgroup category. Subgroup analyses will only be performed on the independent central imaging assessments.

The RECIST 1.1 guidelines state that confirmation of response is not required for randomized Phase III studies that have PFS as the primary endpoint; hence the above summaries will be produced without the requirement for confirmation. However, for completeness all the above

summaries and analyses will be repeated with the requirement for confirmation, these will be considered secondary in nature.

